Study design: This is a randomized study using the same subjects described in Aim 1. Nutritional assessment, physical examination, bioelectrical impedance, laboratories will be performed at baseline, and weeks 2, 4, 6, 8, 12 and 16. Stool samples will be collected on day 3, 7, 14, 17, 21, 28, 42, 56, 84 and 112.

Study timeline: Data collection will be completed at week 16. The stool samples collected during the study period will be used for 16S rRNA sequencing, shotgun metagenomics, and data analysis.

Bioinformatics protocol: Patient characteristics (physical measurements, lean body mass, laboratories, demographic traits) at baseline will be compared using a 2-sided t-test (for numerical variables) or chi-square test (for categorical variables) to evaluate the randomization. 3DFR and FFQ performed at each timepoint will be used to assess the predicted protein content of the patient's diet compared to baseline to evaluate the success of the dietary intervention. Clinical response endpoints significantly associated with HPD in Aim 1 will then be correlated with the abundance of microbes found to be enriched or depleted on a HPD in Aim 2.1. These endpoints will be fitted to multivariate models to adjust for baseline clinical covariates including BMI, age, sex, and smoking status. Spearman correlations will then be calculated for all combinations of residuals for the clinical endpoints and for microbial abundance (using DESeq2 fitted multivariate models from Aim 2.1 to adjust for covariates). Separate correlation analyses will be performed at baseline and each of the time points during treatment.

Microbes that are independently associated with clinical response to a HPD will then be used to create random forests classifiers to predict response. Subjects in the HPD group will be identified as responders if they had a decrease in any of the clinical endpoints that exceeded the predictions of the multivariate model for the NPD group. The sensitivity and specificity of the classifiers will be estimated using 10-fold cross-validation. Classifiers constructed from baseline microbial abundance and microbial data at each time point will be compared to determine the earliest time point when accurate predictions of response are possible.

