The above analytic pipeline will then be applied to the shotgun metagenomics data obtained at baseline and day 112. Gene families and/or metabolic pathways that shift in response to a HPD may be more consistent across diverse populations than abundance of specific microbes such as *Akkermansia* which could vary greatly from person to person⁽⁷⁸⁾. The performance of classifiers constructed from metagenes will be compared to those built from microbial abundance to identify the approach that is most predictive for response.

Expected results/potential pitfalls: We predict that a subset of the HPD-associated microbes and metagenes will be associated with response in the HPD. We also expect that baseline and/or post-dietary intervention abundances of microbial features can be used to generate accurate random forests predictors for clinical response. We used similar bioinformatics approaches to identify the inverse correlation of *Akkermansia muciniphila* with body fat in our rodent model and to predict IBD status in families with pediatric inflammatory bowel disease. Accordingly, we do not anticipate problems performing these analyses.

Human Subjects

1. Risk to Subjects

(a) Human Subjects Involvement and Characteristics:

Approximately 198 healthy volunteers age 30 years and older between BMI of 27 to 40 kg/m² will be able to take part in this study. Pregnant women or women likely to become pregnant during the course of the study may not participate in this study. Female subjects must not be

able to conceive by reason of surgery, radiation, 1 year past the onset of menopause, or an approved method of contraception. No vulnerable subjects will be included in the study. (See the detail in the Research Plan, Proposed Work, Aim 1, Sections of Recruitment, Procedures, and Statistical Analysis)

(b) **Sources of Materials:** See the detail in the Research Plan, Proposed Work, Aim 1, Section of Procedures.

(c) **Potential Risks:**

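### Aim 3 picks its predictor microbes using the outcomes of the same HPD subjects it then cross-validates, so sensitivity and specificity are biased upward, by an amount set by an unstated screening threshold

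*Combined protocol and SAP*

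**What the plan says.** The Bioinformatics protocol of Aim 3 (section 4.C) sets out these steps in order.

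1. Endpoints that differed by diet in Aim 1 are related to the microbes that Aim 2.1 found to respond to the diet: "Spearman correlations will then be calculated for all combinations of residuals for the clinical endpoints and for microbial abundance".
2. The screen is repeated over time: "Separate correlation analyses will be performed at baseline and each of the time points during treatment".
3. "Microbes that are independently associated with clinical response to a HPD will then be used to create random forests classifiers to predict response". The label is responder status among HPD subjects. A subject counts as a responder by beating the NPD-based prediction on at least one endpoint.
4. "The sensitivity and specificity of the classifiers will be estimated using 10-fold cross-validation".
5. "Classifiers constructed from baseline microbial abundance and microbial data at each time point will be compared to determine the earliest time point" that allows accurate prediction.
6. For the sequencing data, "The above analytic pipeline will then be applied to the shotgun metagenomics data obtained at baseline and day 112", and "The performance of classifiers constructed from metagenes will be compared to those built from microbial abundance to identify the approach that is most predictive".

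Aim 3 gives no correlation cut-off, no multiplicity rule for the screen and no definition of independent association. It does not mention selection within folds, a hold-out set or an outside cohort. The nearest statements are elsewhere. Aim 2.1 adjusts its diet comparison for multiplicity, section 3.3 reports q-values for the rat fat-mass correlations, and Aim 3's pitfalls paragraph says "We used similar bioinformatics approaches to identify the inverse correlation of" *Akkermansia muciniphila* with body fat in those rats. The only numeric significance level, p<0.05, is in the Aim 1 secondary analyses.

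**The concern.** Cross-validation gives an honest accuracy estimate only if the held-out subjects played no part in building the classifier. Here the correlation screen uses all subjects' outcomes before any fold is formed. A microbe that correlates with response by chance does so partly because of the subjects later held out, so it appears to predict them. The Aim 2.1 diet filter is not the problem, because it does not use clinical response. The leak comes from the Aim 3 correlation screen.

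Three Aim 3 results depend on these estimates: the accuracy of the classifiers, the earliest time point at which prediction works, and the choice between microbes and metagenes. With a loose screen, the trial could report useful accuracy where none exists. It could also prefer whichever feature set has the larger candidate pool; the documents do not say which that is.

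**Working it through.** **Inputs**
- HPD subjects: 100 randomised per arm (section 4.A, Study Design) with 20% dropout gives 100 × (1 − 0.20) = 80. This reproduces the plan's own figure in Aim 2.1.
- Candidate microbes: not given for humans. Assumed range 30 to 1000. The rat work in section 3.3 gives 114 + 188 = 302.
- Screening rule: not given in Aim 3. Unadjusted p<.05 and Benjamini-Hochberg (BH) q<.05 were both tried.
- Responders: not given. Assumed 69% (55 of 80, so 25 non-responders) or 50%, on one normally distributed endpoint.

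**Mechanism.** Under pure noise, p<.05 keeps about 0.05 × m microbes: 5 of 100, 15 of 300. With n = 80 the cut-off is |r| = t/√(78 + t²) = 1.99/√(78 + 3.96) ≈ 0.22. Every kept microbe therefore correlates at least that strongly in the full 80, and that includes the 80/10 = 8 subjects later held out in each fold.

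**Simulation.** Spearman screen, random forest of 100 trees, stratified 10-fold cross-validation, pooled out-of-fold AUC. Truth comes from 1500 new subjects, and a run that selects nothing scores .50. *As written* means one screen on all subjects; *nested* means the screen is repeated in each training fold.

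No true association, unadjusted p<.05, 69% responders (60 to 150 runs):

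| Candidates | As written | Nested | New subjects |
|---|---|---|---|
| 30 | .535 | .492 | .500 |
| 100 | .642 | .497 | .501 |
| 300 | .742 | .509 | .501 |
| 1000 | .839 | .494 | .496 |

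Sensitivity/specificity at 50% responders was .60/.60 as written against .49/.51 nested (100 candidates), and .70/.68 against .51/.50 (300).

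Three real microbes (r = .4, 150 runs):

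| Screen, candidates | As written | Nested | New subjects | As written minus new |
|---|---|---|---|---|
| p<.05, 100 | .757 | .680 | .682 | .075 |
| p<.05, 300 | .789 | .620 | .637 | .152 |
| BH, 100 | .668 | .629 | .650 | .018 |
| BH, 300 | .646 | .599 | .617 | .029 |

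Unadjusted, the larger pool looks better (.789 against .757) although it predicts worse (.637 against .682). With BH the order is correct.

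**BH under noise.** Something was selected in 14, 18 and 16 of 300 runs (30, 100, 300 candidates), that is 4.7%, 6.0% and 5.3%. In those runs the as-written AUC was .60 to .62 against a true .50; over all runs the mean was about .51.

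**Time points.** One list of 100 microbes, 11 time points (baseline plus ten stool days), no signal. Accurate was taken as AUC .70, an assumption, since the plan gives no cut-off.

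| Screen | Baseline passes, as written (nested) | Any time point passes, as written (nested) |
|---|---|---|
| p<.05 | 25% (0%) | 91% (15%) |
| BH per time point | 1% (0%) | 10% (1%) |
| BH pooled over time points | 0% | 0% |

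BH per time point selected something at one or more time points in 33 of 80 noise runs; pooled BH did so in 2 of 80. With real signal only from day 28, an earlier no-signal time point passed in 85% of runs (nested 13%) unadjusted, and in 3% (nested 2%) with BH. Monte Carlo error on these percentages is up to about 5 points.

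**Other settings** (noise, p<.05, AUC as written with 100 and 300 candidates): backward elimination added, .60 and .71; candidates correlated .5 in blocks of ten, .62 and .72; screen pooling both arms, .58 and .65. A separate simulation with 302 candidates and 50% responders (40 runs) gave sensitivity/specificity .63/.69 against .46/.51 nested at p<.05, and .59/.63 against .48/.52 at p<.01. A linear classifier in place of the forest gave AUC .59–.62, .68–.69 and .81 with 30, 100 and 300 candidates, against .46–.51 nested, so the effect is not peculiar to forests.

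**Precision.** With 25 non-responders, a specificity of 18/25 has an exact 95% interval of .51 to .88. A sensitivity of 44/55 has .67 to .90.

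**The case against.** - **The plan does not rule out nesting.** True. The finding rests on the written sequence and the lack of any safeguard. But an analyst who follows the text performs one screen and then cross-validates.
- **The screen may use both arms.** The text does not restrict it to HPD. Pooling shrinks the leak but does not remove it, because the HPD subjects are still in the screen.
- **The any-endpoint responder rule changes the picture.** This has force. With four endpoints (assumed correlation .5, about 80% responders, 302 candidates), forests at the default vote cut-off gave sensitivity .99 against .98 nested and specificity .04 against .01 at p<.05, so the plan's named measures barely move. That reflects the default cut-off under class imbalance. AUC was still inflated (.61 and .65 with 100 and 300 candidates, against about .47–.50), and a linear classifier with 100 candidates gave specificity .54 against .26.
- **Candidates are filtered first.** Only endpoints significant in Aim 1 and microbes passing the adjusted Aim 2.1 comparison enter. The pool may therefore be small, and with 30 candidates the inflation is slight (.54).
- **A false-discovery-rate screen is the more natural reading, and then little is lost.** On average that is right. But Aim 3 does not commit to such a screen, and the noise runs in which BH selects something are the ones that would yield a classifier to report.
- **Aim 3 has other outputs.** The time course of microbial shifts and the microbe–endpoint correlations are not touched by this point.

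These points limit how large the bias may be. They do not change its direction.

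**Conclusion.** The concern holds. Followed as written, Aim 3 gives upward-biased accuracy because outcome-based selection precedes cross-validation in the same subjects. The size cannot be fixed from the documents. With an unadjusted p<.05 screen and no true signal, AUC rises from .50 to between .54 (30 candidates) and .84 (1000), and the microbe-versus-metagene ranking can reverse if the pools differ in size. With BH the overstatement is about .02 to .03 against new subjects and no reversal was seen. For the time-point comparison the candidate list is the same throughout, so the risk there is falsely high accuracy at an early time point such as baseline.

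These figures assume 80 HPD subjects, one endpoint, an assumed responder share and simulated data; they illustrate the range and do not predict the trial's result. The plan should be changed on this point, but the primary weight-loss analysis is not affected.

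**What to change.** Inside each training fold, repeat every outcome-dependent step that uses HPD subjects: the endpoint residual model, the Spearman screen, the choice of independently associated microbes, and any tuning. Refitting the residual model has not been shown to matter by itself, but it belongs with the other steps because it uses the outcome. A model fitted only to NPD subjects need not be refitted in each fold. Apply this at every time point and to the metagenes.

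Report only the nested sensitivity and specificity, with confidence intervals and the numbers of responders and non-responders. Compare classifiers on the same folds. State the false-discovery-rate threshold for the Aim 3 screen, and whether it applies to each time point separately or to all time points and endpoints together. Define independent association.

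The cost is analysis code and SAP wording, with no new data or visits. Reported accuracy will be lower, and the selected microbes will differ between folds, so the final list needs a separate fit on all subjects.

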The objectives of this proposal, accordingly, are to corroborate data from our preliminary human studies showing that a high protein diet results in body weight loss. We will correlate the observed clinical findings with an understanding of normal and pathological appetite regulatory mechanisms in experimental animals. In order to accomplish the stated goals of this program, we have brought together interdisciplinary collaborations at our VA Medical Center from diverse backgrounds including: microbiome, cell biology, molecular biology, neurophysiology and human clinical investigations, including health services research to investigate the mechanisms regulating feeding behavior and obesity. Our proposal is focused on addressing three hypotheses linking clinical and translational approaches that are critical to understanding the pathophysiology of satiety/obesity.

1. A higher protein replacement diet will result in early satiety signaling and weight loss in obese patients and a differential pattern of postprandial GI hormone release.
2. Patients on the high protein diet will have shifts in the composition and function of their intestinal microbiome.
3. Abundance of specific fecal microbes can be used to predict response to a high protein diet.

C. Specific Objectives.

AIM 1: To Confirm the Hypothesis that a High Protein Diet Reduces Body Weight and Alters the Pattern of Postprandial Gut Hormone Release in Obese Patients.

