Subjects: In a second study, we investigated the effects of an isocaloric high protein diet in non-diabetic obese subjects. In order to determine the effects of isocaloric increased protein meal replacements, 100 obese volunteers were recruited to participate in a 3-month study of meal replacements with either 0.5 g/lb lean body mass/day or 1.0 g/lb lean body mass/day. There were a total of 75 females (41 in group A and 34 in group B) and 25 males (9 in group A and 16 in group B) in the preliminary study. The meal replacements were isocaloric with carbohydrate substituted for protein and dietary fat held constant at 20%. Sixty percent of the subjects have completed the study. The 86 subjects who finished the study are included in this analysis. Mean baseline BMI was 33.63 kg/m^2 (range 27 to 43); mean baseline age was 49.7 years (range 24 to 71). Participants were randomized to either the HP MR treatment group ($n=42$) or standard protein (SP) MR group ($n=46$). Both groups received dietary counseling at baseline, as well as at 2, 4, 8, and 12 weeks. 12-week follow-up data were available in 86 subjects (42 HP, 44 SP). At 12 weeks, the HP and SP groups both lost significant amounts of weight (males: 235.96 ± 7.28 to 221.73 ± 9.34 lbs in HP, 231.5 ± 8.09 to 217.69 ± 7.73 lbs in SP; females: 198.66 ± 4.68 to 188.98 ± 4.53 lbs in HP, 194.19 ± 4.58 to 182.34 ± 5.33 lbs in SP). In the HP versus the SP group, there were no statistically significant differences in changes in weight (-11.1 vs. -11.9 lbs; $p=0.80$), waist circumference (-3.9 vs. -3.0 cm; $p=0.34$), hip circumference (-2.0 vs. -1.08 cm; $p=0.94$), bioelectrical impedance analysis (BIA) fat mass (-7.4 vs. -4.3 lbs; $p=0.17$), total cholesterol (-17.5 vs. -6.3 mg/dL), LDL cholesterol (-11.3 vs. -8.3; $p=0.77$), and HDL cholesterol (+1.3 vs. +0.5 mg/dL; $p=0.62$). A statistically significant reduction in the HP group was observed with regard to fat mass (-1.82 ± 0.66 lbs for HP and 0.24 ± 0.68 for SP, $p=0.0395$) as shown in Fig. 2 and triglyceride concentration (-42.5 vs. -0.3 mg/dL). This analysis demonstrates the potential of increased protein supplementation to result in retention of lean body mass at equivalent weight losses, but longer-term studies are needed to expand on these findings.

C. Alteration of Ghrelin Plasma Levels in Patients' with Neuroendocrine Tumors:

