i. Study Design: This randomized controlled study will assign approximately 200 subjects (100 each) to the following arms (Appendix 1): 1) High protein diet group based on 1 gram of protein per pound of lean body mass, and 2) Standard protein diet group as control based on 0.5 gram protein per pound of lean body mass with same calories. All participants will meet with a registered dietitian, physician or nurse practitioner to assist them with their diet efforts in all the arms. In the study, the percent energy from fat will be held constant at 30% and the differences in the diets relate only to the protein and carbohydrate contents (30% protein and 40% carbohydrate, and 15% protein and 55% carbohydrate respectively). At the initial visit patient will not be calorie restricted but will have standardization of their nutritional macronutrient intake based on their group randomization. At the 2 week visit patient will then begin a 1500 calorie restricted diet with the same macronutrient composition (ie. 30% protein and 40% carbohydrate, and 15% protein and 55% carbohydrate respectively for the high and standard protein groups).

ii. Number of Subjects: Approximately 200 healthy volunteers age 30 years and older with a BMI between 27 to 40 kg/m² will be able to take part in this study.

iii. Estimated Study Duration: Accrual period is 3-4 years; anticipated dropout rate is 20%; and total study duration is approximately 5 years (taking into account data analysis).

iv. Subject Eligibility: Subjects will be assigned an enrollment number after signing the informed consent form. The subjects will complete all the screening tests and procedures as listed. When a subject completes the screening tests and procedures, the subjects will be assigned a randomization number. Subjects will be randomized into one of the two diet groups as described in Appendix 1.

The practitioner at screening will obtain each subject's date of birth, sex, race, medical history, current medications, and smoking and alcohol history. The physician will perform complete physical examinations. Height will be measured using a standardized stadiometer, while the subject stands

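### Aim 3 trains its response classifiers in the high protein arm only and never tests whether the microbe–response association differs between diets, so a generally prognostic microbe that the diet shifts would pass as a predictor of response to high protein

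*Combined protocol and SAP*

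**What the plan says.** The third hypothesis (section 1.B) is that "Abundance of specific fecal microbes can be used to predict response to a high protein diet". The Bioinformatics protocol under Aim 3 (section 4.C) pursues it in four steps.

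1. **Selection.** "Clinical response endpoints significantly associated with HPD in Aim 1 will then be correlated with the abundance of microbes" that Aim 2.1 found to differ on HPD. Aim 2.1 identifies these with a diet-by-time likelihood ratio test on abundance, adjusted for multiple testing.
2. **Adjustment and correlation.** "These endpoints will be fitted to multivariate models to adjust for baseline clinical covariates including BMI, age, sex, and smoking status". Spearman correlations are then taken between endpoint residuals and abundance residuals, at baseline and at each later time point. The text does not say whether these use HPD subjects or both arms.
3. **Responder label.** "Subjects in the HPD group will be identified as responders" if the decrease in any clinical endpoint "exceeded the predictions of the multivariate model for the NPD group".
4. **Classifier.** "Microbes that are independently associated with clinical response to a HPD will then be used to create random forests classifiers to predict response". The classifiers are assessed by 10-fold cross-validation. The same pipeline is then applied to the metagenomic data.

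Both arms share the calorie restriction (section 4.A, Study Design): "At the 2 week visit patient will then begin a 1500 calorie restricted diet with the same macronutrient composition".

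**The concern.** Predicting who loses weight while eating a high protein diet is a different question from predicting who responds to high protein. The second needs evidence that the microbe's association with outcome is stronger under HPD than under the control diet.

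Both arms receive the same calorie target, dietitian contact and meal replacements. In the protocol's own isocaloric pilot (section 3.1.B) mean weight change was -11.1 lb on high protein and -11.9 lb on standard protein (p=0.80). Much of the variation in weight loss within the HPD arm could therefore reflect calorie restriction, adherence or general prognosis. A microbe that tracks any of these can look like an HPD predictor.

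The leading candidate is a plausible case. The protocol expects *Akkermansia* to rise on HPD. It also reports that *Akkermansia* is linked to lower adiposity in other settings, and that in its rat study the inverse correlation with fat mass remained after adjustment for diet. What is at stake is the meaning of the Aim 3 result, although the randomised control data that could settle it are already to be collected.

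**Working it through.** **Inputs from the documents.** The Aim 2.1 expected-results text gives about 80 evaluable subjects per group, which reproduces: 100 × (1 − 0.20) = 80. The Aim 1 sample-size text instead enrols 66 per arm, or 66 × 0.8 ≈ 53 evaluable. The 0.05 two-sided level comes from Aim 1; Aim 3 states none.

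**Assumptions.** The documents give no microbe–response correlation, so r = 0.2 to 0.5 is assumed, equal in both arms. That means no HPD-specific prediction at all. The diet effect on the endpoint is 0 or 0.49 SD (2 × 2.45 / 10, from the Aim 1 inputs).

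**Step 1: HPD-only correlation, for a microbe already selected.** Power ≈ Φ(atanh(r)/√(1.06/(n−3)) − 1.96). For r = 0.3 and n = 80: 0.3095/0.1173 − 1.96 = 0.68, so 75%. Simulation (2,000 runs per setting, covariates removed first) gives 70–72%. At r = 0.2 and 0.4 it gives about 38% and 93%.

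**Step 2: does the NPD cut-point remove this?** One endpoint was simulated, with an HPD subject labelled a responder on beating a covariate-only model fitted in NPD. The table gives the microbe's mean AUC for that label, and for the same label applied in NPD.

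| r in both arms | AUC in HPD | AUC in NPD |
|---|---|---|
| 0.2 | 0.59 | 0.59 |
| 0.3 | 0.63 | 0.63 |
| 0.4 | 0.68 | 0.68 |
| 0.5 | 0.73 | 0.72 |

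The cut-point changes how many are called responders (about 50% with no diet effect, 68% with 0.49 SD). It leaves the general prognostic signal in the label.

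**Step 3: comparing the association between arms.** The standard error of the difference in Fisher z is √(2 × 1.06/77) = 0.166. With equal r the expected difference is zero, so the nominal rejection rate is 5%; simulation gives 3–5%.

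**Step 4: adding the selection filters.** These are taken as unadjusted t-tests at 0.05 with r = 0.3.
- *HPD shifts weight and microbe by 0.5 SD each.* Each filter passes with probability Φ(0.5 × √(80/2) − 1.96) = Φ(1.20) ≈ 0.885. Then 0.885 × 0.885 × 0.72 ≈ 0.56; simulation gives about 57%.
- *HPD shifts weight but not the microbe.* 0.885 × 0.05 × 0.72 ≈ 0.03; simulation gives about 3%.
- *Pilot-like weight difference (0.8 lb over SD 10 = 0.08 SD).* Weight passes its filter in about 8% of runs, and passes with a significant correlation in about 6%.

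**Step 5: power of the between-arm comparison when the microbe works only under HPD (r versus 0).**

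| n per arm | r=0.2 | r=0.3 | r=0.4 | r=0.5 | r for 80% power |
|---|---|---|---|---|---|
| 80 | 23% | 46% | 72% | 91% | 0.43 |
| 53 | 17% | 32% | 54% | 76% | 0.52 |

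These are before any multiplicity adjustment.

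**The case against.** A reader might infer that the control arm is ignored, or used only to draw the responder line. That is not so. It enters in three places: the Aim 1 between-diet test that selects endpoints, the Aim 2.1 diet-by-time test that selects microbes, and the cut-point. A reader might also infer that any microbe tied to weight loss on any 1500 kcal diet would be reported. The filters largely prevent that, as the 3% figure shows. If the pilot's near-equal weight loss recurs, weight itself would usually not reach Aim 3. Both objections stand, and they confine the problem to microbes that HPD shifts. They do not remove it: the filters ask whether diet changes the endpoint and whether diet changes the microbe, not whether the link between the two depends on diet.

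Three further points stand. The roughly 70% is power to detect a genuine association, not a false-positive rate; the error lies in the label attached to it. HPD-only analysis is explicit for the responder label, and hence the classifier, but not for the Spearman step; a pooled correlation would not test HPD-specificity either. Finally, the plan nowhere says it will conclude who should be given a high protein diet. Its expected-results text speaks of features associated with response on HPD, and prediction among people on that diet is a legitimate question.

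**Conclusion.** The concern holds in a limited form. As written, Aim 3 cannot separate a microbe that is prognostic on either calorie-restricted diet from one specific to high protein, and neither the selection filters nor the cut-point supplies the missing comparison. With 80 per arm and an assumed r of 0.3 in both arms, the HPD-only association appears in roughly 70% of trials after selection. Including selection, it appears in about 57% or about 3%, depending on whether HPD shifts the microbe. These figures rest on assumed correlations and shifts, a single endpoint, unadjusted filters and an HPD-only reading of the correlation step. They illustrate the mechanism and do not estimate this trial's error rate. Aim 3 is in effect exploratory, and the primary comparison of weight loss does not depend on it.

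**What to change.** - For each clinical endpoint carried into Aim 3, not weight alone, fit endpoint change on baseline abundance (or metagene), diet and abundance × diet, with the listed covariates, in both arms. Adjust for multiplicity across features and endpoints.
- State which subjects enter the Spearman correlations.
- Report how the classifier trained on baseline HPD data performs in NPD subjects, as a descriptive check only. Poor performance there would not prove specificity, because features chosen for differing between arms may simply be distributed differently in NPD.
- Describe features as predictors of outcome on a calorie-restricted diet unless the interaction supports HPD-specificity.
- Treat on-treatment abundance as association only. Diet itself alters it, so an interaction with it is not a clean test of effect modification.
- Reconcile the 66 and 100 per arm, since interaction power depends on which applies.

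The cost is analysis-plan wording and some extra models on data already planned in both arms. The real downside is power: 46% for r = 0.3 versus 0 and 72% for r = 0.4 versus 0 at 80 per arm, before multiplicity. Few features are likely to be called HPD-specific, and a non-significant interaction should not be read as proof that a microbe is merely prognostic.
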